4.2 Overview of MOR00208

MOR00208 (synonym: XmAb[®]5574), an Fc engineered mAb that binds to the human B-cell surface antigen CD19, is being developed for the treatment of CD19+ lymphoid malignancies. The engineered antibody possesses variable modes of significantly increased tumor cytotoxicity relative to the parent, nonengineered, murine 4G7 anti-CD19 antibody. The increase in binding of MOR00208 Fc to Fc gamma receptors (FcγR) due to engineered mutations significantly enhances in vitro ADCC, ADCP, and direct cytotoxic effects (apoptosis) on tumor relative to the unmodified antibody. MOR00208 has not been shown to mediate complement-dependent cytotoxicity.

In preclinical studies, MOR00208 has demonstrated to significantly enhance in vitro ADCC, ADCP, and direct cytotoxic effects (apoptosis) on CD19+ tumor cell line spanning a broad range of human lymphomas and leukaemias (Burkitt's lymphoma, chronic lymphocytic leukaemia [CLL], hairy cell leukaemia [HCL], CD19+ chronic myeloid leukaemia [CML], DLBCL, and acute lymphoblastic leukaemia [ALL]) expressing different levels of CD19 antigen (15000 to 105000 molecules/cell). Similar effects were also noted on freshly isolated patient CLL or ALL cells and are also expected to translate to primary NHL cells since the expression range reported for ALL and CLL B cells covers the respective range observed for

NHL B cells (Ginaldi et al., 1998; Olejniczak et al., 2006). In vivo, MOR00208 has also shown a superior efficacy compared with its nonengineered version as demonstrated in xenograft models of human lymphoma inducing a significant reduction of tumor growth and increased survival.

Tissue cross-reactivity studies have shown that the pattern and distribution of MOR00208 binding to cynomolgus monkey tissues closely parallels that of human tissues. Flow cytometry experiments with MOR00208 show binding to human and cynomolgus monkey B cells. However, similar results were not observed with B cells of other common laboratory species (rat, mouse, rabbit and dog). Therefore, the range of pharmacology studies was restricted to human and cynomolgus monkey cell-based in vitro systems, CD19+ human B-cell tumor xenograft models in severe combined immunodeficiency (SCID) mice, and to cynomolgus monkeys in vivo. In cynomolgus monkeys, in vivo B-lymphocyte depletion in peripheral blood, bone marrow, spleen and in inguinal lymph nodes, the anticipated response to MOR00208, was observed. Cynomolgus monkeys were judged to be the only relevant common laboratory species for toxicity studies.

The results of studies evaluating the pharmacokinetics, pharmacodynamics and toxicity of MOR00208 are provided in the Investigator's Brochure (IB). The findings in preclinical toxicology studies were limited to the expected pharmacologic effects of MOR00208 and no unanticipated toxicity was observed. These studies include a nonclinical toxicology study conducted in cynomolgus monkeys to support the use of MOR00208 in human clinical trials. The supporting Good Laboratory Practice (GLP)-compliant, multiple-dose toxicology study involved four administrations of MOR00208 over an 8-week time period. Other than the expected dose-related decreases in B-lymphocyte level and in cellularity of spleen tissues, there were no MOR00208-related changes identified in clinical observations, food consumption, body weight, electrocardiography, ophthalmology, urinalysis, coagulation, serum chemistry, and gross anatomic pathology at doses up to 50 mg/kg. In addition, GLP-compliant tissue cross-reactivity studies were performed on normal tissue panels from human and cynomolgus monkey donors. No specific staining to structures other than the expected mononuclear leukocytes, lymphocytes and haematopoietic precursor cells was observed.

Study XmAb[®]5574-01, a Phase I study in patients with CLL/SLL, was the first study of XmAb[®]5574/MOR00208 in humans. The preliminary results of Study XmAb[®]5574-01 showed an acceptable safety profile as well as preliminary activity. One dose-limiting toxicity (DLT) of Grade 4 neutropenia lasting at least 7 days was observed during Study XmAb[®]5574-01 in one patient at the maximum-administered dose (12 mg/kg) out of 16 patients treated at this dose level.

Because the major pharmacologic effect of MOR00208 is B-cell depletion, investigators should be vigilant for adverse events (AEs) associated with the clinical use of B-cell depleting anti-CD20 mAbs as similar effects might be observed with MOR00208.

4.2.1 Clinical Experience with MOR00208

A Phase I study of MOR00208 (XmAb[®]5574-01) in adult patients with relapsed/refractory CLL/SLL was the first study of XmAb[®]5574/MOR00208 in humans. During the course of this study, 27 patients were treated in dose cohorts from 0.3 mg/kg to 12 mg/kg (n=16) intravenously on a weekly schedule for 8 weeks, with an extra dose administered on Day 4. Patients enrolled in the expansion phase of Cohort 6 (12 mg/kg) received an additional

4 monthly doses of MOR00208 after completing the initial 2 cycles of therapy if there was no evidence of disease progression or intolerable drug-related toxicity.

The preliminary antitumor activity of MOR00208 observed in this Phase I study is encouraging and provides support for additional studies. Twenty of 23 patients (87%) with evaluable data in the clinical database had a reduction in their absolute lymphocyte count (ALC; range 2% to 99%), with 17 of 20 (85%) having reductions of >50% from their baseline values. Lymph node size reduction (range 4% to 89%) as assessed by CT scans were observed in 13 of 18 (72%) of patients to date. While the number of patients in this Phase I study is limited to draw definitive conclusions, there appeared to be a dose response relationship with greater reductions in ALCs and nodal size reduction in the higher dose cohorts.

The maximum-tolerated dose (MTD) was not established, since only one DLT occurred. Therefore the selected dose (12 mg/kg) from study XmAb[®]5574-01 will be used in this clinical trial.

4.2.2 Safety of MOR00208

MOR00208 provides a novel mechanism of action that may add to the care of NHL. Based on the available data from the completed clinical study of MOR00208 (Study XmAb[®]5574-01), nonclinical studies and experiments, and literature data on CD19, the sponsor is of the opinion that the potential benefit of MOR00208 outweighs the potential risks. It is expected that the potential risks will be adequately controlled by the design of this trial (eg, by the inclusion and exclusion criteria) and by frequent monitoring of potential adverse drug reactions throughout the entire study. Based on the preliminary results of the clinical study of MOR00208 in patients with CLL/SLL, anticipated possible risks associated with administration of MOR00208 include the following:

One DLT of Grade 4 neutropenia (normal absolute neutrophil count [ANC] at baseline) lasting at least 7 days was observed at the maximum-administered dose of 12 mg/kg.

As of 11 May 2012, 5 serious adverse events (SAEs) have been reported in 5 patients; 2 were considered possibly related to the study drug. One related SAE of febrile neutropenia (Grade 3) occurred in the same patient who experienced the DLT. The second related SAE of tumor lysis syndrome (Grade 3) occurred after the first dose of study drug. The other 3 SAEs were assessed as unrelated by the investigator and included rash (Grade 1), pneumococcal pneumonia (Grade 3), and sinusitis/acute bilateral otitis media (Grade 3).

The most frequent AE was infusion-related reaction in trial XmAb[®]5574-01, which occurred in 12 of 21 (57.1%) patients, despite premedication with antihistamine, acetaminophen and corticosteroids as mandated for the first 3 infusions of MOR00208. All infusion reactions occurred during the patient's first infusion (typically within the first 15 minutes of the start of infusion), as has been described with other B-cell depleting monoclonal antibody therapies in this patient population. Infusion reaction was more frequent in the higher dose cohorts, although infusion reaction did occur in at least one patient in every cohort. The infusion reactions were all Grade 1 or Grade 2 in severity. All patients were able to complete their dose after pausing of the infusion and symptomatic treatment, some with a reduction in the infusion rate.

Leukopenia and neutropenia has been observed in 14% and 24% of patients, respectively, with one patient experiencing Grade 4 neutropenia. Thrombocytopenia has also been reported at a frequency of 14% in patients.

Since a major pharmacologic effect of MOR00208 is B-cell depletion, risks associated with the use of approved anti-CD20 B-cell depleting therapeutics based on their labeling should be considered. These anticipated possible risks include the following: B-cell depletion, absolute lymphocyte reduction, infusion reactions, tumor lysis syndrome, neutropenia/thrombocytopenia, hepatitis B reactivation, progressive multifocal leukoencephalopathy, mucocutaneous reactions and infections.

Anticipated possible risks associated with administration of MOR00208 are described in detail in the IB for MOR00208.

5 STUDY PURPOSE/RATIONALE

MOR00208 has enhanced cytotoxicity against CD19+ tumors in both in vitro and in vivo, and it is expected to provide potent recruitment of immune effector cells as a result of the Fc engineering. MOR00208 is being developed for the treatment of CD19+ lymphoid malignancies. CLL, NHL, HCL and B-precursor ALL represent tumor types that have been well characterized in regard to expression of the CD19 antigen.

Introduction of rituximab into first-line NHL regimens in the recent years has improved cure rate in several NHL subtypes by at least 10%. Despite extensive use of rituximab across a range of NHL subtypes in combination with chemotherapy, as a single agent, or as maintenance therapy, there is still a high unmet medical need for patients with refractory or relapsed NHL (eg, MCL, DLBCL, and FL). (van Oers, 2011; Rummel, 2010; Parekh, 2011)

The B-lymphocyte lineage-specific surface antigen CD19 is the earliest and broadest of the selective B-cell markers, which is highly expressed on the malignant cells in most patients with B-cell NHL. Because of this expression pattern, an anti-CD19 antibody may have clinical utility as a new therapeutic approach to NHL treatment. MOR00208 is an Fc-engineered mAb with significantly enhanced antibody-dependent cell-mediated cytotoxicity (ADCC), antibody-dependent cell-mediated phagocytosis (ADPC), and direct cytotoxic effects (apoptosis) on the tumor relative to the unmodified antibody.

Several mAbs targeting CD19 are currently being evaluated in early-phase clinical trials, demonstrating preliminary efficacy. Data from the Phase I trial in patients with relapsed/refractory CLL/SLL (study XmAb[®]5574-01) demonstrate that MOR00208/XmAb[®]5574 is well-tolerated and has potential clinical benefit. With an enhanced cytotoxicity and safety/tolerability profile, MOR00208 has the potential to be an effective therapy for patients with CD19-expressing B-cell malignancies. The purpose of this study is to evaluate the efficacy and safety of MOR00208 in adult patients with relapsed or refractory NHL.

6 OBJECTIVES

6.1 Primary Objective

- To assess the antitumor activity of single-agent MOR00208 in adult patients with relapsed or refractory NHL who have received at least 1 prior therapy containing rituximab as one of the treatments.

6.2 Secondary Objectives

- To evaluate the duration of response
- To establish safety and tolerability of MOR00208
- To assess the potential immunogenicity of MOR00208
- To evaluate the pharmacokinetics and pharmacodynamics of MOR00208 in patients with relapsed or refractory NHL

7 STUDY DESIGN

7.1 Overall Study Design and Investigational Plan

This is a Phase IIa open-label, multicenter safety and efficacy study of MOR00208, that will enrol approximately 40 to 120 adult patients with refractory or relapsed NHL who have received at least 1 prior therapy containing rituximab.

The study will enrol patients from four different NHL subtypes: FL, DLBCL, MCL and other indolent NHL (MZL, MALT, etc.).

The study will employ a two-stage design where the decision to further enrol any NHL subtype in Stage 2 will depend on best responses after 2 or 3 cycles in Stage 1.

Stage 1 – At least ten patients per NHL subtype (a minimum of 40 patients in total) will be enrolled to receive MOR00208 12 mg/kg weekly for 8 weeks. After 8 and 12 weeks (the latter applicable only for patients with at least SD after 8 weeks) of dosing, patients will be evaluated for response. If in Stage 1 fewer than 2 patients per NHL subtype have a best response of PR or better, then continued enrolment in that cohort will be stopped for futility. If at least 2 patients per NHL subtype have a best response of PR or better, then additional patients will be enrolled into Stage 2 for that subtype cohort.

Any patients with a response of at least stable disease (SD) in Stage 1 will qualify for a further 4 weeks of dosing.

Stage 2 – At least an additional 20 patients will be enrolled for each NHL cohort demonstrating a response in Stage 1. After 8 weeks, the ORR will be evaluated for each NHL cohort.

Any patients with a response of at least stable disease (SD) in Stage 2 will qualify for a further 4 weeks of dosing.

Maintenance treatment - Patients with an ongoing response of at least PR at the end of Cycle 3 (regardless of Stage 1 or 2) may receive further study drug until progression (please see Sections 10.3 and 10.4). Eligible patients will receive a dose of 12 mg/kg MOR00208 either monthly or every second week.

The decision on patient eligibility and dosing frequency for this maintenance treatment will be taken jointly on a case-by-case base by the concerned investigator and the sponsor.

7.2 Study Timeframe

Each patient will participate in the active phases of the study for a minimum of 8 weeks and a maximum of 12 weeks. Patients in maintenance will be treated until progression. The anticipated overall time frame of the study will be 30 months or longer, depending on response in maintenance, until all patients have completed the end of study visit.

7.3 Study Endpoints

Primary endpoint:

1. Overall response rate (CR+PR), assessed as per the 2007 International Working Group (IWG) response criteria

Secondary endpoints:

1. Stable disease (SD), duration of response (DoR), time to progression (TTP), and progression-free survival (PFS)
2. Incidence and severity of AEs
3. Number and proportion of patients who potentially develop anti-MOR00208 antibodies and semiquantitative (anti-MOR00208 antibody titer determination of confirmed positive samples) anti-MOR00208 antibody assessments
4. Pharmacokinetics (C_{max} , t_{max} , C_{pd} [apparent trough serum concentration before dosing], AUC_{0-t} , $AUC_{0-\infty}$, λ_Z , $t_{1/2}$, CL , V_Z)
5. Absolute and percentage change from baseline in measurements of B-, T- and NK cell populations
6. Evaluation of AEs and ORR stratified by baseline CD19 expression on malignant lymphoma cells
7. Evaluation of AEs and ORR stratified by Fc γ RIIIa and Fc γ RIIa polymorphism

8 POPULATION

The study population will consist of adult patients with relapsed or refractory B-cell NHL who have received at least 1 completed cycle of combination therapy with rituximab + chemotherapy or at least 4 weekly administrations of rituximab as monotherapy.

The planned sample size is at least 40 patients in Stage 1 (at least 10 patients per NHL subtype) and up to a maximum of 80 additional patients in Stage 2 (approximately 20 patients enrolled to each NHL subtype that continues to enrol into Stage 2). The entire study will enrol between 40 to approximately 120 patients, depending on decision to stop enrolment for futility.

The investigator or his/her designee must ensure that only patients who meet the following inclusion and exclusion criteria are offered enrolment into the study:

8.1 Inclusion Criteria

1. Patients are male or female ≥ 18 years of age.
2. Patients have a histologically confirmed diagnosis according to the Revised European American lymphoma/World Health Organization (REAL/WHO) classification, of the following B-cell lymphomas:
 - a. FL
 - b. Other indolent NHL (eg, MZL/MALT) (see section 17.7)
 - c. DLBCL
 - d. MCL

NOTE: For transformed lymphomas, the subtype at screening (not at initial diagnosis) is relevant for the assignment to the respective subtype.

3. Patients' NHL must have progressed after at least 1 prior rituximab-containing regimen.
4. Patients have at least one site of measurable disease by magnetic resonance imaging (MRI) or computed tomography (CT) scan defined as at least one lesion that measures at least 1.5×1.5 cm,

Exception:

For patients with MCL only, patients with nonmeasurable disease but evaluable sites (bone marrow, spleen, peripheral blood, gastrointestinal tract) can be enrolled.

5. Patients who have previously received an autologous stem cell transplantation must be at least 4 weeks post-transplant before study drug administration and must have exhibited a full haematological recovery.
6. Patients must have discontinued previous monoclonal antibody therapy (except rituximab) or radioimmunotherapy administration for at least 60 days before study drug administration.
7. Patients should be off rituximab for at least 14 days before the screening visit and be confirmed to have either no response or have disease progression after rituximab treatment.
8. Patients with DLBCL had a positive [^{18}F]fluorodeoxyglucose-positron emission tomography (FDG-PET) scan at baseline (Cheson 2007 response criteria).
9. Patients have a life expectancy of > 3 months.
10. Patients must have an Eastern Cooperative Oncology Group (ECOG) performance status of < 3 .

11. Patients must meet the following laboratory criteria at screening:
 - a. Absolute neutrophil count (ANC) $\geq 1.0 \times 10^9/L$
 - b. Platelet count $\geq 75 \times 10^9/L$ without previous transfusion within 10 days of first study drug administration
 - c. Hemoglobin ≥ 8.0 g/dL (may have been transfused)
 - d. Serum creatinine < 2.0 x upper limit of normal (ULN)
 - e. Total bilirubin $\leq 2.0 \times$ ULN
 - f. Alanine transaminase (ALT) and aspartate aminotransferase (AST) $\leq 2.5 \times$ ULN
12. If a female of childbearing potential, a negative pregnancy test must be confirmed before enrolment and use of double-barrier contraception, oral contraceptive plus barrier contraceptive must be used during the study and for 3 months after the last dose, or confirmation of having undergone clinically documented total hysterectomy and/or oophorectomy, tubal ligation.
13. If a male, an effective barrier method of contraception must be used during the study and for 3 months after the last dose if the patient is sexually active with a female of childbearing potential.
14. The patients are able to comply with all study-related procedures, medication use, and evaluations.
15. The patients are able to understand and give written informed consent and comply with the study protocol.

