17.4 Response Criteria

The response criteria in this study are those defined in the table below. All of them are based on the International Working Group Response Criteria (2007).

Table 8 Response Criteria

Response	Definition	Nodal masses	Spleen, liver	Bone marrow
CR	Disappearance of all evidence of disease	a) FDG-avid or PET positive prior to therapy; mass of any size permitted if PET negative b) Variable FDG-avid or PET negative; regression to normal size on CT	Not palpable, nodules disappeared	Infiltrate cleared on repeat biopsy; if indeterminate by morphology, immunohistochemistry should be negative
PR	Regression of measurable disease and no new sites	≥ 50% decrease in SPD of up to 6 largest dominant masses; no increase in size on CT a) FDG-avid or PET positive prior to therapy; one or more PET positive at previously involved site b) Variable FDG-avid or PET negative; regression on CT	≥ 50% decrease in SPD of nodules (for single nodule in greatest transverse diameter); no increase in size of liver or spleen	Irrelevant if positive prior to therapy; cell type should be specified
SD	Failure to attain CR/PR or PD	a) FDG-avid or PET positive prior to therapy; PET positive at prior sites of disease and no new sites on CT or PET b) Variable FDG-avid or PET negative; no change in size of previous lesions on CT		
Relapsed disease or PD	Any new lesion or increase by ≥ 50% of previously involved sites from nadir	Appearance of a new lesion(s) > 1.5 cm in any axis, ≥ 50% increase in SPD of more than one node, or ≥ 50% increase in longest diameter of a previously identified node > 1cm in short axis Lesions PET positive if FDG-avid lymphoma or PET positive prior to therapy	> 50% increase from nadir in the SPD of any previous lesions	New or recurrent involvement

Abbreviations: CR, complete remission; FDG, [¹⁸F]fluorodeoxyglucose; PET, positron emission tomography; CT, computed tomography; PR, partial remission; SPD, sum of the product of the diameters; SD, stable disease; PD, progressive disease

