7.3.4.2 Central Read

Additionally a central radiology read of scans will be performed by SYNARC/BioClinica. The revised IWG criteria definitions [4] will also be applied. Details of the central read are described in the Independent Review Charter, Version 1.0, 01-JUL-2013, provided by SYNARC.

The independent reviewers (two primary radiologists) will be presented with all time points sequentially in chronological order, and will provide assessments for each time point. For the

overall tumor assessment of the central read a slightly different terminology is used:

- CR - Complete response
- PR - Partial response
- SD - Stable disease
- PD - Relapsed or progressive disease
- NE - Non-Evaluable (can be applied if repeated measurements cannot be applied for reasons such as inadequate or missing imaging and when progression/relapse cannot be assigned for the visit overall response)
- ND - No Disease (this category is used if there is no tumor and there was no tumor at baseline)

Once the independent reviews for all time points in the course of the study have taken place, all time points for a particular patient will be again reviewed together by the two independent reviewers in a global patient review over all time points. In their global patient review the two independent reviewers will determine:

- best overall response (defined as best response the subject had since treatment started taking into account scheduled and unscheduled visits)
- date of the best overall response
- duration of best overall response (calculated by the system as time from first response to progression if patient is PD at a specific visit)
- date when progression/relapse occurred

Finally, an adjudicator radiologist will perform adjudication, in case there is any discrepancy in the global patient review of the two primary radiologists. The adjudicator will review both initial readings and will record a new review that will agree with either of the duplicate reviews. Thus, the adjudicator will need to agree to the complete reading of one of the primary radiologists (all assessments by visit and all variables from corresponding global review). A mandatory comment will need to be recorded. The adjudicated reading results will be considered as the results for the involved patients.

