There may be rare cases where the two primary radiologists disagree in some of the overall assessments by visit, but agree in the global patient review. In these cases no adjudication will be performed. Thus for the overall assessment by time point, descriptive tables will be based on

the following results:

- Assessment of the reader the adjudicator agrees with, in case adjudication was performed
- Worst response assessment of the two primary radiologists at each visit in case no adjudication was performed

All other variables described below are only based on the variables from global review which are adjudicated in case of discrepancies between the two primary radiologists. The term “central reviewer” used below refers to the adjudicator in case adjudication is performed or to the primary radiologists (in case global patient review of the two primary radiologists are identical and no adjudication is necessary).

In case any anti-tumor treatments other than MOR00208 are given before end of study (see also section 8.3), it is regarded as protocol non-compliance. Following a conservative approach for statistical analysis, the following steps will be implemented by [REDACTED] biostatistics: tumor assessments of the two primary radiologists after start of other anti-tumor treatment which are non-PD will not be taken into account, whereas assessments of PD will still be taken into account. Moreover, if the date of best overall response as provided by the adjudicator is after start of anti-tumor treatment, the date will be set to missing and the best overall response to “not evaluable”. This ensures that a progress is still included in the analysis if an anti-tumor treatment has been started based on clinical progression, but the image confirming PD was done at a later time point. A response after start of anti-tumor treatment will, however, not be counted for best overall response.

Tumor Response categories (Central Read) will be evaluated in terms of absolute and percentage frequencies by visit

Best overall response (Central Read) will be directly provided by the central reviewer (SYNARC uses the terminology best overall response or best response).

Overall response rate (ORR) (Central Read) will be evaluated as the rate of patients who have a best overall response of PR or CR.

Overall rate of SD (disease control rate) (Central Read) will be evaluated as the rate of patients who have a best overall response of PR, CR or SD.

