9. EFFICACY ANALYSES

All efficacy analyses will be provided for the ITT Population. All efficacy analysis will be done using both the central radiology and local (i.e., investigator) assessment. Kaplan-Meier plots will be generated for all time-to-event analyses (i.e., for the Time to Progression, Progression-Free Survival, Duration of Response).

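### MCL patients may enter without measurable disease, but Table 8 gives some of them no route to PR and the central read may class them as No Disease, while all stay in the ORR denominators

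*Protocol*

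**What the plan says.** **Entry.** Protocol 8.1 criterion 4 asks for a lesion of at least 1.5 x 1.5 cm on CT or MRI. MCL alone is exempted: "patients with nonmeasurable disease but evaluable sites (bone marrow, spleen, peripheral blood, gastrointestinal tract) can be enrolled". SAP 3.2 repeats the exemption.

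**Response.** Protocol 17.4 Table 8 describes PR in general as "Regression of measurable disease and no new sites". By column, the PR entries are:
- Nodal masses: at least a "50% decrease in SPD of up to 6 largest dominant masses; no increase in size on CT".
- Spleen and liver: at least a "50% decrease in SPD of nodules (for single nodule in greatest transverse diameter); no increase in size of liver or spleen".
- Bone marrow: "Irrelevant if positive prior to therapy; cell type should be specified".

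There is no column for peripheral blood or gut. CR does have a marrow entry (infiltrate gone on repeat biopsy) and a spleen entry (no longer palpable). SAP 7.3.4.1 binds the investigator to these criteria.

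**Central read.** SAP 7.3.4.2 describes a radiology read of scans with the categories CR, PR, SD, PD, NE and ND. On ND it says "this category is used if there is no tumor and there was no tumor at baseline". Central ORR "will be evaluated as the rate of patients who have a best overall response of PR or CR".

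**Denominator.** SAP 9 states: "All efficacy analyses will be provided for the ITT Population". SAP 9.1 applies the ITT denominator to the primary ORR.

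**Futility.** Protocol 14.9 and SAP 5 stop a subtype with fewer than 2 responders in 10, and give a 14.9% chance of stopping at a true ORR of 30%.

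**The concern.** Entry was widened for one subtype, but the response criteria were not widened with it. Some MCL patients can therefore sit in the ORR denominator with only part of the endpoint, CR, open to them. On the central read, some may have neither CR nor PR open.

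Three results are exposed: the MCL ORR on both reads, the pooled ORR, and the MCL Stage 1 decision. A low MCL response rate could then reflect partly who was enrolled and partly how active the drug is, and the planned tables would not let a reader separate the two.

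The concordance analysis in SAP 9.1 is affected as well. It divides the diagonal counts by all patients assessed, and ND has no counterpart among the investigator categories. SAP 9.1 excludes only patients whom the central reviewers did not evaluate. An ND patient has been evaluated, so stays in.

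Nothing else in the SAP covers this. The one ORR sensitivity analysis drops patients with no post-baseline assessment, SAP 9.3 has no subgroup by measurability, and SAP 12 is silent. SAP 10.2 adds that marrow findings other than CD19 will not reach the statistical analysis, so a CR resting on marrow clearance could not be checked there.

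**Working it through.** **Step 1. Which patients lack a PR route.** The sites named in criterion 4 are set against Table 8 and the central categories.

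| Disease at entry | PR in Table 8 | CR in Table 8 | Central read |
|---|---|---|---|
| Marrow only | none | open (marrow cleared) | ND if scans show no tumor |
| Blood only | none (no column) | open through the general definition | ND if scans show no tumor |
| Spleen enlarged, no nodules | none (size must only not increase) | open (not palpable) | depends on what readers see |
| Gut, no mass | none (no column) | open through the general definition | ND if not visible |
| Nodes below 1.5 cm, or splenic nodules | may be open (no minimum size in the PR rule) | open | not ND if seen |

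**Step 2. The plan's own figures.** Inputs are n = 10, p = 0.30 and a stop at 0 or 1 response.

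P(X ≤ 1) = 0.7^10 + 10 × 0.3 × 0.7^9 = 0.0282 + 0.1211 = 0.1493. The stated 14.9% reproduces. The exact (Clopper-Pearson) lower limit for 9/30 is 14.7%, also as stated.

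**Step 3. Stopping chance with k patients who lack a PR route.** Let k of the 10 MCL patients respond with probability q (CR only) and the other 10 − k with probability 0.30. Responses are then the sum of Binomial(10 − k, 0.30) and Binomial(k, q). Both k and q are assumptions.

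For k = 2 and q = 0.10, the 8 others have P(0) = 0.0576 and P(1) = 0.1977. The 2 patients have P(0) = 0.81 and P(1) = 0.18.

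P(total ≤ 1) = 0.0576 × 0.81 + 0.1977 × 0.81 + 0.0576 × 0.18 = 0.217.

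| k of 10 | q = 10% | q = 5% | q = 0 (limit) | q = 30% |
|---|---|---|---|---|
| 0 | 14.9% | 14.9% | 14.9% | 14.9% |
| 1 | 18.0% | 18.8% | 19.6% | 14.9% |
| 2 | 21.7% | 23.6% | 25.5% | 14.9% |
| 3 | 26.0% | 29.4% | 32.9% | 14.9% |
| 4 | 31.0% | 36.2% | 42.0% | 14.9% |

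**Step 4. Expected ORR.**
- MCL, 10 patients, k = 2: (8 × 0.30 + 2 × q)/10 = 26% at q = 10% and 24% at q = 0.
- Pooled, 40 patients, k = 2: (38 × 0.30 + 2 × q)/40 = 29.0% at q = 10% and 28.5% at q = 0.
- MCL, if 30 were enrolled, k = 6: 26% at q = 10% and 24% at q = 0. The latter is 7.2 expected responders; 7/30 has an exact lower limit of 9.9%, against 14.7% for 9/30.

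**Step 5. Central read.** If an ND patient would otherwise have had a 30% chance of response, each one lowers the expected central ORR of a 10-patient cohort by 0.30/10 = 3 points, from 30% to 27%. In the concordance matrix, an ND patient whom the investigator scores CR, PR or SD is off the diagonal by construction. A later central PD for a new lesion is the exception.

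**The case against.** The strongest reply is that the primary endpoint is CR plus PR on the investigator read, and CR stays open to these patients. A reader might infer that they cannot meet the primary endpoint, and so take the q = 0 column as the effect on it. Table 8 does not support that. For the investigator read, q = 0 is a limit. This part of the reply stands.

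Other parts also stand:
- A reader might infer that no exempted patient can score PR. Criterion 4 defines measurability by a 1.5 x 1.5 cm lesion, while the PR rule sets no minimum size, so small nodes or splenic nodules may qualify.
- A reader might infer that every exempted patient is ND throughout the central read. ND needs an absence of tumor on baseline imaging, and spleen or gut disease may be visible. Best overall response comes from a separate global review governed by a charter that is not among the documents.
- The 14.9% is conditional on a true ORR of 30% and is correct on that condition. The number of affected patients could be zero. That their CR rate lies below 30% is assumed, not shown.
- Counting unscorable patients as nonresponders is conservative, and dropping ND patients from the denominator can only raise the central ORR. That argues for a sensitivity analysis, not for replacing the ITT figure.
- SAP version 4.0 is dated April 2019 and foresees a July 2015 cutoff, so the Stage 1 decision can hardly be altered now.
- Results are reported by subtype and no inferential testing is planned, so the separate FL and other indolent NHL estimates are untouched.

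These points limit the size and reach of the concern. They do not supply a PR rule for the affected patients, a stated handling of ND, or an analysis that would show the effect.

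**Conclusion.** The gap is real and narrow. MCL patients with marrow-only, blood-only, diffuse splenic or non-mass gut disease have no written route to PR, and on the investigator read can respond only by CR. Those with no tumor on baseline scans fall under ND centrally. They remain in the ITT denominator of central ORR, and they are discordant with any investigator CR, PR or SD unless later coded PD.

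This may lower the MCL and pooled ORR and raise the MCL stopping chance. With 2 such patients in 10, the chance moves from 14.9% to 21.7% at an assumed 10% CR rate, with 25.5% as the limit. These sizes rest on assumed values of k and q and on a 30% ORR in the remaining patients. If no such patient was enrolled, or if their CR rate equals 30%, the stopping chance stays at 14.9%.

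A reader might go further and conclude that the plan's 14.9% is wrong, or that the MCL cohort was bound to fail. The documents support neither conclusion. They show that the plan cannot separate low activity from a response that could not be scored as PR.

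**What to change.** In SAP 9.1:
1. Keep the ITT investigator ORR and the ITT central ORR as the main analyses.
2. Add, for MCL and overall, a supportive ORR on both reads in patients with measurable disease at baseline (a lesion of at least 1.5 x 1.5 cm). Name the source of the baseline flag, because SAP 9.2 presents lesion size separately for two central readers, who may disagree.
3. Show ND as its own row in the central response table. Give central ORR without ND patients as a sensitivity analysis only.
4. Exclude baseline-ND patients from the concordance matrix and report their number.
5. In the study report, give the number of Stage 1 MCL patients with nonmeasurable disease beside the MCL futility outcome and the 14.9%.

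The cost is some SAP wording and a few extra rows, with no change to eligibility, treatment or the primary analysis. SAP 4.1 still foresees later analyses and a report addendum, so there is a place for them. The drawback is a smaller MCL denominator, and so a wider interval, in the supportive estimates.
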